5. STUDY TREATMENTS

5.1. Description and Handling of Study Treatments

5.1.1. Test Product

AT-527 will be provided by the Sponsor as 550 mg tablets.

5.1.2. Control Product(s)

Matching placebo tablets for AT-527 will also be provided by the Sponsor.

AT-527 (or placebo) will be administered along with local supportive SOC therapy per local/institutional practices or guidelines. Other than restrictions listed in [Section 5.8](#), SOC will not be dictated by the protocol.

Protocol Number: AT-03A-001

5.1.3. Packaging and Labeling

The Sponsor will be responsible for ensuring that study drugs (active and placebo) are manufactured in accordance with applicable Good Manufacturing Practice regulations and requirements. The labels for the study drug(s) will meet applicable local regulatory requirements.

5.1.4. Storage and Handling

Study drugs should be stored under the conditions described on the label.

5.2. Method of Assigning Subjects to Treatment Groups

A unique subject number will be assigned to each subject at Screening. Once assigned, it will not be reassigned to another subject. Once eligibility is confirmed, subjects will then be randomly assigned to a treatment group (active vs. placebo) according to a randomization list, generated by the designated independent biostatistician. This will be through a centralized randomization process and eligible subjects may also receive a unique randomization number linked to a treatment assignment.

5.3. Blinding

Treatment assignments will be blinded to the investigator, research staff, subjects, CRO and Sponsor for the entire study, unless unblinding is mandated by a DSMB recommendation. The study blind will be broken upon completion of the clinical study and after the study database has been locked. The only exceptions will be those described with the DSMB analyses and procedures ([Section 10.1](#)).

During the study, the blind may be broken for an individual subject by the investigator only in emergencies or when knowledge of a subject's treatment group is necessary for further subject management. Although not necessary in the case of an emergency, the investigator should discuss the specific case with the Sponsor prior to unblinding. The date and reason for breaking the blind must be recorded.

As noted in [Section 10.1](#), the Sponsor, CRO, and clinical site personnel will remain treatment-blinded to the data reviews by the DSMB, unless the DSMB promulgates a study guidance recommending study halt for efficacy, safety, or futility.

5.4. Dosing and Administration

5.4.1. Dispensing

Based on their randomization assignment, blinded study drug (active or placebo) will be assigned depending on treatment arm. Designated site staff will dispense the blinded study drugs (active or placebo) to each subject at each dispensing day/time. The date and time of each dose must be recorded. If subjects are discharged from the hospital prior to study drug completion, they will be provided with study drug to be taken at home to complete their assigned treatment course.

Protocol Number: AT-03A-001

5.4.2. Administration Instructions

Part A

Subjects will take one (1) tablet (550 mg AT-527 or placebo x 1) administered approximately every 12 hours (i.e. BID) for the 5-day treatment period.

Part B

Subjects will take two (2) tablets (550 mg AT-527 or placebo x 2) administered approximately every 12 hours (i.e. BID) for the 5-day treatment period.

Study drugs will be taken orally and should be taken at approximately the same time each day, ideally within an approximate 2 hour window (as a guidance). The drugs may be given with water. Previous studies indicate no appreciable effect of food on AT-527 absorption, so study dosing can be done between or during mealtimes. Regular daily timing is preferred, to consistently achieve dose intervals of approximately 12 hours. Dosing on Day 1 can occur at any time of day (AM or PM).

If a dose is missed, subjects should be instructed to take the missed dose(s) of study drugs as soon as possible during the same day. Subjects should never double the next dose with a missed dose.

5.4.3. Treatment Compliance

Doses will be administered under the supervision of designated site staff to ensure treatment compliance.

If subjects are discharged from the hospital prior to study drug completion, they will be provided with study drug to be taken at home to complete their assigned treatment course, and compliance will be confirmed by follow-up telephone call or potentially an at-home visits by trained medical professional(s) (if feasible).

5.5. Study Drug Accountability

Complete and accurate records of all study drugs must be kept. These include acknowledgment of receipt of each shipment of study product, subject dispensing records and returned or destroyed study product.

At the end of the study, all unused study drugs and containers will be returned to the Sponsor (or designee) or destroyed, per the instruction of the Sponsor. Documentation confirming drug accountability will be reviewed over the course of the trial.

5.6. Stopping Rules

5.6.1. Safety Stopping Rules for Individual Subjects

Treatment will be discontinued in any subject who experiences any one of the following:

- progression to requirement for mechanical ventilation or ECMO
 - Note: For any subject who progresses to mechanical ventilation or ECMO, study treatment should be discontinued, as there is no IV form of the study drug. The subject may then receive any other available treatments, with

Protocol Number: AT-03A-001

continued study observation for post-treatment safety data to hospital discharge or death as locally feasible. Subjects who have completed or discontinued study drug may be treated with any other available therapeutic agent, as locally allowed. If the agent is investigational it should be an agent that has institutional Ethics Committee or Research Committee approval, or FDA EUA.

- confirmed elevation of ALT or AST $> 3 \times$ baseline with direct bilirubin $> 2 \times$ ULN or INR increased from baseline and $> 1.5 \times$ ULN, without evident alternative cause for these elevations
- confirmed new onset \geq grade 3 serum creatinine ($> 1.8 \times$ ULN and $> 2 \times$ baseline), or decreased creatinine clearance to < 60 mL/min
- any SAE, or a grade 4 AE or clinically significant confirmed grade 4 laboratory abnormality for an individual subject which is considered by the investigator to have a reasonable possibility of relatedness to study drug
 - Note: To warrant treatment discontinuation for a study subject, a **confirmed grade 4 laboratory abnormality should have clinically significant findings** expected to be associated with the laboratory abnormality. Subjects with isolated asymptomatic laboratory abnormalities, without any clinical correlations, are allowed to remain on treatment with continued monitoring according to the preference of the investigator. Also, subjective clinical symptoms not reflecting major organ dysfunction, such as severe headache, may or may not warrant treatment discontinuation in the judgement of the investigator.
- Pregnancy

A confirmed value is defined as one that is found to have a similar value at the next subsequent test. Any of the above laboratory results and all \geq grade 3 new onset laboratory abnormalities must be repeated as soon as possible, preferably within 24 hours upon reporting of the initial value. If a grade 3/4 lab abnormality is determined to be clinically significant, it should be reported as an AE and should include an assessment of causality. Definitions of clinical significance of laboratory abnormalities are summarized in [Section 7.1.1](#). For any grade 3/4 AE or laboratory abnormalities, the site must enter the data into the Electronic Data Capture (EDC) system within 24 hours.

Subjects who prematurely discontinue study treatment should complete early termination (ET) assessments at the time of treatment discontinuation, as described in [Table 6-1](#). However, these subjects should be encouraged to remain in the study and maintain the same protocol schedule and assessments as described in [Table 6-1](#). This will allow for continued follow-up for key study outcome data.

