8.2.5. Safety Endpoints

Safety-related comparisons for the two treatments in this trial will include:

- Proportions of subjects experiencing SAEs
- Proportions of subjects with fatal outcomes
- Proportions of subjects experiencing AEs
 - Overall, and by body system as coded by MedDRA
- Proportions of subjects experiencing drug-attributed AEs
- Proportions of subjects experiencing graded laboratory abnormalities
 - With abnormality grades defined in the referenced DAIDS table
- Proportions of subjects discontinuing study for AEs
- Proportions of subjects discontinuing treatment for AEs

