## COVID-19 Statistical Analysis Plan

DAIDS Term	Laboratory Test	No Event	Grade 1	Grade 2	Grade 3	Grade 4
Creatinine, High	Creatinine ( $\mu$ mol/L)	Criteria for Grade 1 - 4 not met	1.1 to 1.3 x ULN	> 1.3 to 1.8 x ULN OR Increase to 1.3 to < 1.5 x participant's baseline	> 1.8 to < 3.5 x ULN OR Increase to 1.5 to < 2.0 x participant's baseline	$\geq$ 3.5 x ULN OR Increase of $\geq$ 2.0 x participant's baseline
Creatinine Clearance, Low	Creatinine Clearance (mL/s)	Criteria for Grade 2 - 4 not met	NA	< 1.5 to 1 OR 10 to < 30% decrease from participant's baseline	< 1 to 0.5 OR 30 to < 50% decrease from participant's baseline	< 0.5 OR $\geq$ 50% decrease from participant's baseline or dialysis needed *

Document: \\[REDACTED]net\enterprise\Apps\sasdata\SASb\SAS\Atea\_Pharmaceuticals\AT-527\SZA63631\Biostatistics\Documentation\SAP\AT-03A-001\_SAP\_V1.0\_COVID\_SAP\_PA7.doc

Author: [REDACTED]

Version Number: V1.0

Version Date: 15Apr2021

Template No.: CS\_TP\_BS016 Revision 6

Effective Date: 02Dec2019

Reference: CS\_WI\_BS005

Copyright © 2009, 2010, 2012, 2016, 2018, 2019 [REDACTED] All rights reserved. The contents of this document are confidential and proprietary to [REDACTED] Holdings Inc. and its subsidiaries. Unauthorized use, disclosure or reproduction is strictly prohibited.

COVID-19 Statistical Analysis Plan

ATEA Pharmaceuticals  
Protocol AT-03A-001

Page 73 of 77

DAIDS Term	Laboratory Test	No Event	Grade 1	Grade 2	Grade 3	Grade 4
Cardiac Troponin I, High	Troponin I (ng/L)	Criteria for Grade 4 not met	NA	NA	NA	Levels consistent with myocardial infarction or unstable angina as defined by the local laboratory *
Glucose Fasting, High	Glucose (mmol/L)	< 6.11	6.11 to < 6.95	6.95 to < 13.89	13.89 to < 27.75	≥ 27.75
Glucose, Low	Glucose (mmol/L)	≥ 3.55	3.05 to < 3.55	2.22 to < 3.05	1.67 to < 2.22	< 1.67
Cholesterol Fasting, High	Total cholesterol (mmol/L)	< 5.18	5.18 to < 6.19	6.19 to < 7.77	≥ 7.77	NA
Triglycerides Fasting, High	Triglycerides (mmol/L)	< 1.71	1.71 to 3.42	>3.42 to 5.7	>5.7 to 11.4	> 11.4
Creatine Kinase, High	Creatine kinase (IU/L)	< 3 x ULN	3 to < 6 x ULN	6 to < 10x ULN	10 to < 20 x ULN	≥ 20 x ULN

Document: \\[REDACTED]\net\enterprise\Apps\sasdata\SASb\SAS\Atea\_Pharmaceuticals\AT-527\SZA63631\Biostatistics\Documentation\SAP\AT-03A-001\_SAP\_V1.0\_COVID\_SAP\_PA7.doc

Author: [REDACTED]

Version Number: V1.0

Version Date: 15Apr2021

Template No.: CS\_TP\_BS016 Revision 6

Effective Date: 02Dec2019

Reference: CS\_WI\_BS005

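### The creatinine stopping rule is labelled grade 3 or higher, but its numbers select only part of DAIDS grade 4 and so stop fewer subjects than the label

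*Protocol*

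**What the plan says.** Protocol 5.6.1 lists the events that discontinue treatment in an individual subject. The renal bullet has two limbs:

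- **Creatinine limb.** A confirmed, new-onset result at or above "grade 3 serum creatinine". A bracket then requires the value to be both above 1.8 × ULN and above 2 × baseline.
- **Clearance limb.** Alternatively, "decreased creatinine clearance to < 60 mL/min".

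Neither limb asks for a judgement of causality. A separate bullet in the same section covers grade 4 laboratory abnormalities. It applies only if the abnormality is confirmed, clinically significant and considered possibly related to study drug.

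The grading scale is DAIDS v2.1. Protocol 7.1 and 7.1.1 use it for adverse events, and Protocol 8.2.5 reports laboratory abnormalities "With abnormality grades defined in the referenced DAIDS table". SAP Appendix 4 reproduces the rows:

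- **Creatinine, High.** Grade 3 is "> 1.8 to < 3.5 x ULN OR Increase to 1.5 to < 2.0 x participant's baseline". Grade 4 starts at 3.5 × ULN or at 2.0 × baseline.
- **Creatinine Clearance, Low.** Grade 3 is below 1 and down to 0.5 mL/s (below 60 and down to 30 mL/min), or "30 to < 50% decrease from participant's baseline". Grade 4 includes any fall of 50% or more.

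**The concern.** The label and the bracket are two different rules for one mandatory stop. DAIDS joins its two creatinine criteria with OR, and the bracket joins them with AND. The bracket takes its ULN multiple (1.8) from the lower limit of grade 3, but its baseline multiple (2) from the lower limit of grade 4. The protocol nowhere says that a rule narrower than its label was intended.

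A site that works from the grade and a site that works from the numbers can reach opposite decisions on the same subject. The protocol treats renal safety as a point to watch. Section 1.4 notes nephrotoxicity with some nucleoside analogues (though not as a class effect) and lists renal monitoring among its safeguards, and Part B doubles the dose to 1100 mg BID.

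**Working it through.** **Notation.** Let u = value / ULN and b = value / baseline.

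| Rule | Source | Condition |
|---|---|---|
| Bracket | Protocol 5.6.1 | u > 1.8 AND b > 2 |
| DAIDS grade 3 (if not grade 4) | SAP Appendix 4 | 1.8 < u < 3.5 OR 1.5 ≤ b < 2.0 |
| DAIDS grade 4 | SAP Appendix 4 | u ≥ 3.5 OR b ≥ 2.0 |
| Label, i.e. grade 3 or higher | union of the two rows above | u > 1.8 OR b ≥ 1.5 |

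**Step 1: which grades can meet the bracket?** The bracket needs b > 2, and b ≥ 2.0 alone is grade 4. So every value that meets the bracket is grade 4 and no grade 3 value can. Grade 4 values with u ≤ 1.8 or with b ≤ 2 fail it. The bracket is thus a strict subset of grade 4, and the mismatch runs in one direction only.

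**Step 2: set check on a grid.** Take u from 0.5 to 6.0 and b from 1.0 to 4.0 in steps of 0.05.

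| DAIDS grade | Grid points | Meeting the bracket |
|---|---|---|
| Below 3 | 270 | 0 |
| 3 | 930 | 0 |
| 4 | 5571 | 3360 |

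These counts show coverage of the grade definitions. They are not subject frequencies.

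Individual cases that the bracket misses:

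- 0.6 to 1.0 × ULN (b = 1.67): grade 3
- 1.0 to 1.9 × ULN (b = 1.9): grade 3
- 0.5 to 1.1 × ULN (b = 2.2): grade 4

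**Step 3: does the clearance limb close the gap?** At fixed age and weight, Cockcroft-Gault clearance is proportional to 1/creatinine. After an f-fold rise the new clearance is baseline / f, so the limb acts only if baseline < 60f:

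- f = 1.5: 60 × 1.5 = 90 mL/min
- f = 1.6: 60 × 1.6 = 96 mL/min
- f = 2.0: 60 × 2.0 = 120 mL/min

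Entry requires at least 60 mL/min. The limb therefore recovers subjects between 60 mL/min and these limits, and misses those at or above them.

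**Step 4: two worked subjects.**

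*Example 1.* Baseline clearance 100 mL/min, 1.6-fold rise. New clearance is 100 / 1.6 = 62.5 mL/min, a fall of 37.5%. This is grade 3 on the creatinine row (1.6 × baseline, for any value below 3.5 × ULN) and grade 3 on the clearance row (fall between 30% and 50%). The bracket fails because 1.6 is not above 2, and the clearance limb fails because 62.5 is not below 60.

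*Example 2 (assumed subject).* Male, 45 years, 100 kg, creatinine 0.9 mg/dL.

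- Baseline clearance: (140 − 45) × 100 / (72 × 0.9) = 146.6 mL/min.
- After a 2.1-fold rise, creatinine is 0.9 × 2.1 = 1.89 mg/dL, which is grade 4 on the baseline criterion.
- Against an assumed ULN of 1.1 to 1.3 mg/dL: 1.89 / 1.1 = 1.72 and 1.89 / 1.3 = 1.45, both below 1.8, so the bracket fails.
- New clearance: 146.6 / 2.1 = 69.8 mL/min, so the clearance limb fails too.

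**Step 5: does another bullet act?** The grade 4 laboratory bullet does not cover grade 3. For grade 4 it needs clinical significance and judged relatedness, and its note lets subjects with isolated, symptom-free laboratory findings stay on treatment.

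**Step 6: how long is the window?** Dosing lasts 5 days, and Table 6-1 puts on-treatment safety laboratory tests at Days 2 and 5. Section 5.6.1 defines a confirmed value as one repeated at the next test. A Day 5 result will usually be confirmed only after dosing ends, so the rule acts mainly on the Day 2 result and its repeat.

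**The case against.** The arithmetic is not in dispute; its weight is. The strongest counter-argument has four parts.

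- **The numbers may be the rule.** They follow the label directly, so most sites would probably apply them, and the fault would then be a loose label. The INR part of the liver bullet also pairs a change from baseline with a ULN multiple. This reading is possible, but the text does not state it, and under it the words grade 3 describe nothing. It is a reason to offer the second remedy, not to leave the conflict in place.
- **Other safeguards exist.** All new-onset abnormalities of grade 3 or higher must be repeated, preferably within 24 hours, and grade 3/4 data entered within 24 hours (5.6.1). Section 5.7 lets the investigator withdraw a subject at any time. These are monitoring and discretionary steps. They soften the consequence but do not restore a mandatory stop.
- **The reach is small.** The exposed group needs a high baseline clearance and an early confirmed rise, and the second example rests on an assumed subject. This stands. It limits the size of the problem without removing it.
- **Matching DAIDS exactly has a price.** A rise from 0.6 to 0.9 × ULN is 1.5 × baseline, so it would force a stop wholly within the normal range. This is a fair argument for also requiring an absolute elevation, and it bears on which remedy to choose.

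**Conclusion.** The concern holds. As written, the numeric creatinine criterion excludes every DAIDS grade 3 value and some grade 4 values, although its label promises grade 3 and above. The clearance limb leaves a gap for 1.5-fold rises at baseline clearance of 90 mL/min or more and for 2.0-fold rises at 120 mL/min or more.

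The set comparison rests only on Protocol 5.6.1 and SAP Appendix 4. The clearance limits further assume Cockcroft-Gault with age and weight unchanged between tests. The patient values and ULN range in Example 2 are assumptions. The number of subjects affected cannot be estimated, because the documents give neither a creatinine distribution nor a frequency of such rises. The short dosing period keeps the practical effect modest, but a mandatory safety threshold should have one meaning.

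**What to change.** Choose one of two edits to the renal bullet in Protocol 5.6.1:

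1. **Keep the label and correct the numbers.** Replace the bracket with: > 1.8 × ULN or ≥ 1.5 × baseline. This equals DAIDS grade 3 or higher in SAP Appendix 4. Changing only AND to OR is not enough, because rises of 1.5 to < 2.0 × baseline at or below 1.8 × ULN would still be missed.
2. **Keep the numbers and delete the label.** If the narrower threshold was intended, for instance to avoid stopping for rises within the normal range, remove the reference to grade 3 and state the numeric threshold alone.

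The text change is one line, although Protocol 11.1 sends amendments to the IRB/IEC for approval. Option 1 would lead to some additional discontinuations during the 5-day course, in a number the documents do not allow to be estimated. Option 2 changes no decision at a site that already follows the numbers.

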5.6.2. Study Stopping Rules

COVID-19 is a protean, sometimes fatal, illness for which the spectrum of disease-related signs and symptoms is still being delineated. Aside from principal involvement of the respiratory tract, with potentially severe pneumonia, it is increasingly clear that clinical manifestations can also include multi-organ manifestations due to a hyper-coagulopathy with widespread thromboembolic processes in other body organs - liver, heart, brain, etc. With this perspective, a

Protocol Number: AT-03A-001

multi-organ variety of clinical AEs and laboratory abnormalities can be expected from COVID-19 study populations, regardless of treatment. Effective therapies may reduce COVID-19 disease manifestations over time, but the wide variety of COVID-19 related AEs and laboratory abnormalities will be seen in both active- and placebo-treated subjects until therapy mitigates the disease or the disease spontaneously resolves.

This clinical trial will be paused for a DSMB review of safety data, for any of the following reasons:

- Death in any subject in which the cause of death is judged to have a reasonable possibility of relatedness to the study drug by the investigator.
- The occurrence in any subject of a life-threatening SAE whose causal relationship is judged to have a reasonable possibility of relatedness by the investigator.
- >20% of the enrolled subjects experience clinically significant grade 3/4 AEs or clinically significant confirmed grade 3/4 laboratory abnormalities considered by the investigator to have a reasonable possibility of relatedness to the study drug.

Additional rules will be applied for the first two enrolling cohorts of 20 subjects each in Part A. For each 20-subject cohort, the study will also be paused for a DSMB safety review for any of the following reasons:

- Two (2) occurrences of grade 3 or higher clinical AEs that are assessed to have a reasonable possibility of relatedness to the study drug by the investigator.
- Two (2) occurrences of a clinically significant grade 3 or higher laboratory abnormality assessed to have a reasonable possibility of relatedness to the study drug by the investigator.

For any of the above circumstances, a pause in further study enrollment will be triggered. The DSMB will then review unblinded safety data for the referenced events, to determine if active treatment poses an appreciably greater risk for these events or other concerning safety events compared to placebo treatment. If the latter appears to be the case, the Sponsor will collect and review all the available safety data with the DSMB, clinical investigators, and regulatory authorities (including US FDA), to obtain an overall risk assessment for active vs. placebo treatment, and agreement on a plan forward.

Collaborative decisions on study stoppage will include consideration of the relative occurrence of the given AE or lab abnormality in active- vs. placebo-treated subjects, and the clinical severity of the specific AE or lab abnormality. For example, in consideration of the severity gradations in the Division of AIDS (DAIDS) table, transient episodes of grade 3-4 headaches, anorexia, fatigue/malaise, myalgias/arthritis, psychologic manifestations, and other AEs and lab abnormalities in the DAIDS table, are likely to be observed with placebo recipients and active-treated subjects in this clinical trial; and early datasets could by chance show more events for active-dosed subjects vs. placebo recipients. In those circumstances an agreed plan for further study conduct will be achieved by a collaborative safety review involving the Sponsor, DSMB, clinical investigators, and regulatory authorities (including US FDA).

Protocol Number: AT-03A-001

In addition, this study could be stopped by a DSMB recommendation for study stoppage due to efficacy, safety, or futility as described in [Section 10.1](#).

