This antiviral signal was further interrogated in the subset of patients with higher baseline viral loads (VL) above the median of $5.26 \log_{10}$ as compared to placebo (see figure below). Similarly, antiviral activity of AT-527 was also observed in this subset of patients, further suggesting a signal that warrants additional study. As the AT-527 group had lower viral loads at baseline in this sub-set of patients, an exploratory analysis with the baseline viral load threshold lowered to $5.0 \log_{10}$ was conducted in which both treatment groups had similar mean viral loads at baseline. Results were consistent and showed a similar trend toward earlier viral clearance in the AT-527 group.

Protocol Number: AT-03A-001

Quantitative SARS-CoV-2 RNA, mITT with Baseline VL \geq median (5.26 log₁₀ copies/mL)

[figure not shown]

Patients in the AT-527 arm achieved SARS-CoV-2 clearance (no detectable RNA or target not detected (TND)) as early as Day 2 (6%), Day 8 (7%) and Day 10 (33%), Day 12 (31%) compared to 0% in the placebo arm at the same timepoints. By Day 14 (last viral sampling study day) approximately 47% of patients in the AT-527 arm and 22% in the placebo arm had no detectable RNA virus (TND) (see figure below).

Protocol Number: AT-03A-001

Qualitative SARS-CoV-2 RNA, mITT Patients with Baseline VL \geq median (5.26 log₁₀ copies/mL)

AT-527 dosed as 550 mg BID for 5 days was generally well-tolerated in this population. There were no drug-related SAEs. Non-serious AEs were equally distributed across treatment arms. Most were mild-to-moderate in severity and assessed as not related to the study drug. No clinically significant abnormal ECGs were reported. No safety concerns or newly determined risks were identified.

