- In Part A, a cohort of 20 subjects was initially enrolled to preliminarily assess the safety of the 550 mg BID dosing regimen. Enrollment was paused after the first 20 subjects, until the DSMB conducted a safety review. Upon DSMB review, a second cohort of 20 subjects was enrolled in Part A and enrollment was paused until the DSMB conducted a safety review of these data. Again, the DSMB allowed the study to continue without modification.
- In order to perform the interim analysis, Part A enrollment was paused by the Sponsor after 81 subjects were randomized. As described in [Section 1.1](#), no additional subjects will be randomized in Part A with implementation of Amendment 8.
- Part B subjects will be randomized (1:1) to one of the two following arms:

Disease Severity	Treatment Duration	Dosing Arms	
Moderate	5 days	active	1100 mg AT-527 administered every ~12 hours (10 doses) + SOC
		placebo	AT-527 placebo administered every ~12 hours (10 doses) + SOC

*Randomized 1:1 (active:placebo)

- Up to an additional 110 subjects will be enrolled in Part B.
- An additional DSMB safety review will occur when 50% of the Part B subjects have been enrolled.

For each interim safety review, pooled safety data will be reviewed by the DSMB. The DSMB will alert the Sponsor if there are any safety concerns for active-treated subjects compared to placebo recipients.

Protocol Number: AT-03A-001

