3.2. Number of Subjects

- The study is planned to enroll 190 subjects with moderate COVID-19 and risk factors for poor outcomes; determination of the targeted sample size is described in [Section 8.2](#).
 - Part A: 81 subjects were randomized at the time of the Part A interim analysis.
 - Part B: Up to an additional 110 subjects will be enrolled in Part B.

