10. DATA COLLECTION, RETENTION, AND MONITORING

10.1. Data Safety Monitoring Board (DSMB)

A DSMB, comprising two independent clinical experts and an independent statistician, will be established to periodically assess safety and potential risk/benefit.

The DSMB will conduct planned serial safety reviews during the course of the study.

Protocol Number: AT-03A-001

For interim safety reviews during Part A of the study, enrollment will be paused at the following timepoints:

- After the first 20 subjects to assess safety of the 550 mg BID dosing regimen
- After the second 20 subjects

For interim safety reviews during Part B of the study, enrollment will not be paused but a safety review will be conducted at the following timepoint:

- After 50% of the Part B subjects have been enrolled.

In addition to these planned meetings, the DSMB may schedule ad hoc meetings during the course of the study.

During their reviews of data, the DSMB will have the authority to unblind data to the DSMB members, if necessary for assessing safety for an individual subject or across treatment arms. Additional details will be described in the DSMB charter. Regardless, the Sponsor, CRO, and clinical site personnel will remain treatment-blinded to all data reviewed by the DSMB, unless the DSMB promulgates a study guidance recommending study halt for efficacy, safety, or futility.

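### The >20% safety pause rule counts all enrolled subjects, so Part A's 81 dilute it for 1100 mg: with no Part A or placebo events it cannot fire before about half of Part B

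*Protocol*

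**What the plan says.** Protocol section 5.6.2 introduces the study-level rules with "This clinical trial will be paused for a DSMB review of safety data, for any of the following reasons". The third reason is that ">20% of the enrolled subjects experience clinically significant grade 3/4 AEs or clinically significant confirmed grade 3/4 laboratory abnormalities" which the investigator considers possibly related to study drug. The other two are a related death and a related life-threatening SAE. If any rule is met, "a pause in further study enrollment will be triggered".

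The same section then says "Additional rules will be applied for the first two enrolling cohorts of 20 subjects each in Part A". These pause the study at two related events of grade 3 or higher within a 20-subject cohort, counted separately for clinical AEs and for clinically significant laboratory abnormalities. They do not extend to Part B.

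On numbers, section 3.2 states "Part A: 81 subjects were randomized at the time of the Part A interim analysis" and section 3.1 states "Up to an additional 110 subjects will be enrolled in Part B", randomized 1:1 between 1100 mg BID and placebo. Section 10.1 plans one DSMB review in Part B, at 50% of its enrollment: "For interim safety reviews during Part B of the study, enrollment will not be paused but a safety review will be conducted". It leaves further detail to the DSMB charter, which is not among the documents.

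**The concern.** The rule is a share of enrolled subjects in the trial, and nothing limits it to a Part. The rules that follow it are expressly limited to Part A, so 5.6.2 was written with both Parts in view. Taken as written, the denominator for the doubled dose starts at 81 people who received 550 mg or placebo and cannot contribute an 1100 mg event. Part B placebo subjects are added to it.

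In Part B this is the only automatic pause trigger for related grade 3/4 events that are neither fatal nor life-threatening. The cohort rules have lapsed and the planned review leaves enrollment open. The weakening falls in the first half of Part B, when a pause would protect the most subjects still to be enrolled.

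**Working it through.** The protocol gives no operating characteristics for this rule, so there is no planned figure to reproduce.

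**Inputs.** Part A: 81 randomized (3.2). Part B: up to 110, 1:1 (3.1). Threshold: more than 20% of enrolled (5.6.2), with enrolled read as randomized. Planned DSMB review: 50% of Part B, i.e. 55 subjects (10.1). The number of qualifying Part A subjects is not stated. Section 1.1 reports no drug-related SAEs and says of the non-serious AEs "Most were mild-to-moderate in severity and assessed as not related to the study drug". I call that number a and vary it.

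**Formulas.** With n Part B subjects enrolled:

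- Pooled count needed = smallest integer above 0.2 × (81 + n).
- Needed from 1100 mg recipients = that number − a − Part B placebo events.
- Exposed to 1100 mg = n/2 under an even split.
- Part B-only count needed = smallest integer above 0.2 × n.

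**No Part A or placebo events.**

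| Part B enrolled | Exposed to 1100 mg | 0.2 × (81 + n) | Pooled count needed | Part B-only count needed |
|---|---|---|---|---|
| 20 | 10 | 20.2 | 21 | 5 |
| 40 | 20 | 24.2 | 25 | 9 |
| 54 | 27 | 27.0 | 28 | 11 |
| 56 | 28 | 27.4 | 28 | 12 |
| 110 | 55 | 38.2 | 39 | 23 |

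The pooled rule can fire only when n/2 > 0.2 × (81 + n), i.e. 0.3n > 16.2, so n > 54. The first even n is 56, with 28 of 28 affected. If the active arm is one ahead, it is n = 53 (27 of 27 against 26.8). At n = 110 the requirement is 39/55 = 71%.

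**Some Part A events, none on Part B placebo.** The earliest even n for a = 1, 2, 3, 4, 5 is 52, 48, 46, 42, 38, in each case only if every 1100 mg recipient is affected. At n = 54 the need runs from 27 down to 23 of 27 (100% to 85%). At n = 110 it runs from 38 down to 34 of 55 (69% to 62%).

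**A background rate in Part A and in Part B placebo.**

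- 5%, n = 54: about 4 + 1 events, so 28 − 5 = 23 of 27 (85%).
- 5%, n = 110: about 4 + 3, so 39 − 7 = 32 of 55 (58%).
- 10%, n = 54: about 8 + 3, so 28 − 11 = 17 of 27 (63%).
- 10%, n = 110: 39 − 8.1 − 5.5 = 25.4, about 25 of 55 (46%).

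**Chance that the count meets the trigger at n = 54**, just before the planned review, with X ~ Binomial(27, p) and p the true related grade 3/4 rate on 1100 mg:

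| Denominator and background | Needed of 27 | p = 30% | p = 40% | p = 50% |
|---|---|---|---|---|
| Part B only, no placebo events | 11 | 16% | 54% | 88% |
| Pooled, a = 0, no placebo events | 28 | 0 | 0 | 0 |
| Pooled, a = 5, no placebo events | 23 | <0.02% | <0.02% | <0.02% |
| Part B only, 10% background (3 placebo events) | 8 | 59% | 90% | 99% |
| Pooled, 10% background (8 + 3 events) | 17 | 0.04% | 1.3% | 12% |

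**The case against.** **The wording could mean the current Part.** Part A is closed and Part B is a separate dosing cohort, so counting within Part B is a possible reading, and the unseen charter may say so. The ambiguity is real. But 5.6.2 is what investigators and ethics committees work from, and it limits one set of rules by Part and not this one. An automatic trigger should not depend on interpretation.

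**The zero-event case is the extreme.** Investigators judge relatedness blinded, so related events on placebo are plausible, and 5.6.2 itself expects grade 3/4 events in both arms. At a 10% background the pooled rule needs 17 of 27 at n = 54. That softens the headline, but the gap stays wide: 12% against 99% at a 50% event rate.

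**Arm imbalance.** Randomization uses variable-size blocks stratified by region (section 8), so the active arm could run further ahead. With no other events, an active excess of 4, 5 or 8 moves the earliest firing point to n = 48, 47 or 42. The statement that it cannot fire before about half therefore needs a near-even split. Even then, all 1100 mg recipients (26, 26 or 25) must be affected.

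**Other safeguards.** A single related death or related life-threatening SAE still pauses the trial, and related grade 4 events may qualify under the latter. Individual stopping rules (5.6.1), 24-hour entry of grade 3/4 data, ad hoc DSMB meetings, DSMB or sponsor authority to stop and the mid-Part B review all remain. This stands and narrows the gap. But the individual rules stop dosing in one subject, not enrollment, and ad hoc review is discretionary.

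**Remaining effect.** The SAP changes form of March 2022 says the study is ending early and Part B will only be listed. That limits what a change can still achieve. It does not make the rule sound as written.

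**Conclusion.** The concern holds and should be fixed. As written, the 81 Part A subjects dilute the >20% rule for the dose Part B tests. With no Part A or placebo events and a near-even split, it cannot fire until 53 to 56 of 110 Part B subjects are enrolled, and then only at a 100% event rate on 1100 mg. At full enrollment it needs 71%. With one to five Part A events the earliest point is n = 52 to 38, still at 100%.

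The result rests on the literal pooled denominator, enrolled meaning randomized, and an assumed range for the unstated Part A count. One backstop is weakened and the other safeguards are untouched.

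**What to change.** In 5.6.2 and the DSMB charter, state that the >20% is counted among subjects enrolled in the Part currently being dosed, so Part B subjects only for 1100 mg. Keep the event definition and the 20% value. If the charter already defines a Part B denominator, 5.6.2 should say the same.

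The cost is one clause in each document, with the usual ethics committee submission for a protocol amendment. The downside is a possible extra DSMB review on few events early in Part B: one affected subject would trigger it among the first 4, and two among 5 to 9. If that is unwanted, start the count at the 20th Part B subject, where 5 are needed.

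This restores a working trigger for large excesses. It does not make 20% sensitive to moderate ones: with no placebo events, a 30% rate on 1100 mg would meet it only 16% of the time at n = 54. Whether 20% suits the new dose is for the sponsor and the DSMB to decide.
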